8.4 Transition Period (In-Center/In-Home dialysis treatment)

Over the four-week transition period, Investigational site personnel will confirm the Subject is stable in the new care environment, has been appropriately trained on the set up and use of the Tablo Hemodialysis System and has satisfactorily completed the items of the patient skills assessment. The Subject will be responsible for device set up and initiating therapy under the supervision of study personnel In-Center during the first portion. The second portion of the transition period In-Home will be supervised at the discretion of the investigator.

Prior to treatment, pre-dialysis vitals, including body weight, temperature, blood pressure, and heart rate (pulse), will be collected. Using established center protocols, the subject or identified trained individual

will: 1) prep Subject's dialysis access (i.e., catheter, fistula or graft) using trained aseptic technique, and 2) perform cannulation of the fistula or graft, or connection to a catheter.

Once all pre-treatment steps are complete, the Subject will initiate dialysis and monitor their treatment according to the center protocol. During treatment, vital signs, including blood pressure measurements and heart rate (pulse), will be collected every 30 minutes for the first hour, then hourly until the completion of the treatment.

Post-treatment vitals, including body weight, temperature, blood pressure and heart rate (pulse), will also be collected.

During therapy, each Subject is encouraged to limit food and water intake. Subjects will document any alarms that occurred which required intervention (such as medication or saline administration or a change in treatment parameters), under what conditions they occurred, and final resolution. A summary of alarm occurrence will be tabulated from data transmitted to Outset Medical. Subjects will also document any signs or symptoms that they experienced during treatment.

Each Subject will be prescribed dialysis therapy for four times per week with no inter-dialytic (end of treatment period to start of next treatment period) period greater than 2 days. No isolated ultrafiltration will be available on the device during the study.

8.5 Treatment Period 2 (In-Home dialysis treatment)

Subject will administer dialysis therapy at home during Treatment Period 2 according to the Investigator's instruction. After device setup, the Subject will take his/her pre-dialysis vitals, including body weight, temperature, blood pressure, and heart rate (pulse), and confirm the dialysis prescription.

Using established center protocols, the subject or identified trained individual will: 1) prep Subject's dialysis access (i.e., catheter, fistula or graft) using trained aseptic technique, and 2) perform cannulation of the fistula or graft, or connection to a catheter.

Once all pre-treatment steps are complete, the Subject will initiate dialysis and monitor their treatment according to the center protocol. During treatment, vital signs, including blood pressure measurements and heart rate (pulse), will be collected every 30 minutes for the first hour, then hourly until the completion of the treatment.

Post-treatment vitals, including body weight, temperature, blood pressure and heart rate (pulse), will also be collected.

During therapy, each Subject is encouraged to limit food and water intake. Subjects will document any alarms that occurred which required intervention (such as medication or saline administration or a change in treatment parameters), under what conditions the alarms occurred, and final resolution. A summary of alarm occurrence will be tabulated from data transmitted to Outset Medical. Subjects will also document any signs or symptoms that they experienced during treatment.

Each Subject will be prescribed dialysis therapy for four times per week with no inter-dialytic (end of treatment period to start of next treatment period) period greater than 2 days. No isolated ultrafiltration will be available on the device during the study.

8.6 Weekly Visits during the In-Center and In-Home Treatment Periods

Weekly visits for each Subject will be conducted by a study staff member during Treatment Periods 1 (In-Center) and 2 (In-Home). During this weekly visit, signs and symptoms experienced by the Subject both since the last dialysis treatment as well as those experienced during dialysis treatments will be reviewed, as well as compliance to treatment time. The study staff member will also review the definitions of adverse and serious adverse events and re-educate the Subject where necessary.

8.7 Laboratory Assessments

Each Subject will be required to provide approximately 120ml or 8 tablespoons of total blood for the duration of the trial to monitor the Subject's blood chemistry. Samples will be collected as outlined in Appendix B.

For weekly draws to calculate the Urea Reduction Ratio (URR) and thereby quantify dialysis treatment adequacy, collect approximately 54-57ml into **Yellow top or serum separator tubes** in increments of 3ml or 0.6 teaspoons for pre and post dialysis treatment BUN.

For pre BUN, prior to connecting to Tablo or administering heparin bolus, fill appropriate tubes according to the standard of care.

For post BUN, pull the sample at the conclusion of therapy by reducing the blood pump speed to 100 ml per minute. Allow one minute to elapse at that blood flow rate, then collect the sample according to the standard of care.

Additionally, at least twice during each treatment period (Treatment Period 1, In-Center and Treatment Period 2, In-Home), collect both chemistry and hematology, and iron indices as specified (see Appendix B for tests and timing).

For chemistry, collect approximately 54-57ml into **Tiger top** or serum separator tubes in increments of 3ml or 0.6 teaspoons, according to the standard of care.

For hematology, collect approximately 12ml in **Lavender top** tubes in increments of 3ml or 0.6 teaspoons according to the standard of care.

During visits when both Chemistry and CBC labs will be drawn, the recommended draw order is **Tiger top** or serum separator **followed** by **Yellow top** or serum separator. All samples will be processed according to reference laboratory requirements. No blood samples will be stored or used for permanent or immortal cell lines.

8.8 Follow Up

Subjects' treatment modialities will be followed for up to 5 years post study completion.

8.9 Device Malfunction

Device malfunctions are instances where the device does not perform as intended. During device set-up, treatment administration and post-treatment, site personnel and/or the Subject will be requested to inspect and identify any defective parts. The study Investigator (or designee) will notify the Sponsor and comply with Sponsor procedures for returned goods.

8.10 Subject Assessment

Each Subject will be asked to complete questions weekly regarding whether or not the device was easy to use, whether assistance was needed, and the length of recovery time required post treatment. In addition, the Subject will be asked to complete a questionnaire regarding signs and symptoms experienced during each treatment (see section 9.2 Recording Adverse Events).

8.11 Device Water and Dialysate Testing

During device installation in-center and in-home and monthly thereafter, water and dialysate samples will be collected and tested. Samples above the limits ($\geq 100CFU/ml$ or ≥ 0.50 EU/ml for dialysate and ≥ 100 CFU/ml or > 0.25EU/ml for water) may be considered device failures. If results are above the action limit

Page 23 of 40

Outset Medical

 $(\geq 50 \ CFU/ml \ or \geq 0.50 \ EU/ml \ for \ dialysate \ and \geq 50 \ CFU/ml \ or > 0.25 \ EU/ml \ for \ water)$ a chemical disinfection cycle will be run, a new sample will be drawn and new test results obtained. In addition, Sponsor will review the culture and disinfection logs and determine if the system should be removed from patient use. If above the action limit upon retesting the device will be removed from use.

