4.1 Tablo[™] Hemodialysis System Overview

Incoming water is pretreated in the Sediment and Carbon Filtration subsystem a. This pre-treated water then passes through the Reverse Osmosis (RO) system where polyamide thin-film composite membranes purify the incoming water. This process reduces the levels of chemical and microbial contaminants, producing water for dialysis meeting AAMI/ANSI/ISO 13959 limits. After cycling through the WPS, the purified water enters the Dialysis Delivery System.

The Dialysis Delivery System de-aerates the treated water, then proportions and mixes in acid and bicarbonate concentrates. The resulting dialysate fluid passes through an ultrafilter to assure the dialysate meets the AAMI/ANSI/ISO 11663 limits for microbial contaminants. During routine use, both heat and chemical disinfections are utilized throughout both the Water Purification System and the Dialysis Delivery System to maintain water quality. Heat disinfection and chemical disinfection are performed at defined intervals to reduce the microbial burden that may occur in the fluid path and components.

The Cartridge, consisting of a single-use disposable blood tubing set attached to an Organizer, draws blood from the Subject through interaction with a peristaltic pump, and passes the blood through a dialyzer before returning the treated blood to the Subject. The disposable Cartridge is provided sterile. Therefore, neither the blood tubing set nor Organizer is treated with heat or chemical disinfectant.

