4.2 Principle of Operation

During treatment, the water purification system produces dialysis-quality water, which is delivered to the Dialysis Delivery System where the water is mixed with the proportioned concentrates. The resulting dialysate passes through the ultrafilter and enters the dialyzer.

Within 24 hours following treatment the Tablo Console performs a heat disinfection cycle, during which the fluid path components of both the water purification system and the Dialysis Delivery System are heated. After the heat disinfection cycle is completed, the Console shuts down and any residual hot water in the Console cools. The Console performs a pre-treatment cycle before the next treatment begins during which the entire fluid path is flushed with freshly purified water.

In addition to post-treatment heat disinfection, a chemical disinfection cycle is performed periodically. During this cycle, a peracetic acid type of disinfectant (e.g. Peracidin) disinfects the fluid path. After the chemical disinfection, the fluid path is rinsed until no detectable residual peracetic acid is present (as determined by conductivity measurements). After rinsing the chemical disinfectant, another heat disinfection cycle is performed as previously described. The complete disinfection cycle concludes when the Console shuts down and any remaining water cools. Prior to the next treatment, the user is prompted by the user interface to perform a water test to ensure no residual disinfectant remains.

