7.6 Subject Discontinuation and Replacement

Every Subject should remain in the study until completion of the required follow-up period. Subjects may voluntarily withdraw from the study at any time with or without reason and it will not have any negative impact on subsequent treatment. Conceivable reasons for Subject discontinuation may include, but are not limited to, the following:

- **Subject Withdrawal:** Subject participation in this clinical study is voluntary. The Subject may choose to discontinue participation (refuse all subsequent testing) at any time without loss of benefits or penalty.
- **Discontinuation:** Subject participation may be discontinued by the Subject or Investigator because of a treatment modality change, organ transplant, transfer, death or prolonged hospitalization.
- **Investigator Termination:** The Investigator may terminate the Subject's participation without regard to the Subject's consent if the Investigator believes it is medically necessary.
- Exclusion Criterion Discovered After Enrollment: A small number of Subjects may be enrolled despite meeting an exclusion criteria due to timing of study required clinical procedures. This will be documented by the study personnel on the Case Report Form (CRF), and will be considered a protocol deviation.

- Lost-to-Follow-up: If the Subject fails to complete eight consecutive treatments, regardless of whether or not they fall into a single treatment period or a total of up to eight missed treatments, consecutive or not, per period, but has not formally withdrawn from the study, he or she will be considered lost-to-follow-up. The data from this Subject is still eligible for the intent to treat dataset. Site personnel should make all reasonable efforts to locate and communicate with the Subject, at each contact time point, including:
 - A minimum of two telephone calls to contact the Subject should be attempted. Each attempt should be recorded in the Subject's medical record, including date, time, and initials of site personnel attempting the contact.
 - o If telephone calls are unsuccessful, a certified letter should be sent to the Subject.

If the above-mentioned attempts at communicating with the Subject are unsuccessful, the Subject will be considered lost-to-follow-up.

NOTE: If the Subject can be contacted, study treatments will resume at the point when the last treatment was conducted.

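### Protocol 8.11: the endotoxin action limits equal the device-failure limits, so endotoxin, unlike bacterial count, gives no early warning

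*Protocol*

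**What the plan says.** Protocol 8.11 sets the sampling schedule: "During device installation in-center and in-home and monthly thereafter, water and dialysate samples will be collected and tested". It then defines two tiers.

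- **Possible device failure.** Dialysate at ≥100 CFU/ml or ≥0.50 EU/ml; water at ≥100 CFU/ml or >0.25 EU/ml. The endotoxin part reads "or ≥ 0.50 EU/ml for dialysate and ≥ 100 CFU/ml or > 0.25EU/ml for water) may be considered device failures".
- **Action limit.** Dialysate at ≥50 CFU/ml or ≥0.50 EU/ml; water at ≥50 CFU/ml or >0.25 EU/ml.

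When the action limit is reached, "a chemical disinfection cycle will be run, a new sample will be drawn and new test results obtained". The sponsor also reviews the culture and disinfection logs and decides whether the console should leave patient use. The last step is mandatory: "If above the action limit upon retesting the device will be removed from use".

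Some controls do not depend on any test result. Heat disinfection runs within 24 hours of a treatment, and 4.2 adds that "In addition to post-treatment heat disinfection, a chemical disinfection cycle is performed periodically". Section 4.1 describes a dialysate filter: "The resulting dialysate fluid passes through an ultrafilter to assure the dialysate meets the AAMI/ANSI/ISO 11663 limits for microbial contaminants". Section 4.4.2.5 has the console remind users of maintenance, which includes ultrafilter replacement.

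**The concern.** A separate action tier is useful when it sits below the failure tier, so that rising contamination is treated before the sample counts as a possible failure. For bacterial count, 8.11 does this: readings from 50 to just under 100 CFU/ml prompt a response. For endotoxin that band is empty in both fluids. Neither document gives a lower endotoxin trigger elsewhere or says why endotoxin is handled differently.

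What is at stake is patient exposure between monthly samples, including the eight weeks of self-administered dialysis at home. Pyrogenic reaction is one of the eight pre-specified events in the primary safety endpoint (Protocol 9.1.5), so the subject matters to the trial. That link is qualitative, and I claim no effect on the event count.

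**Working it through.** **1. The two tiers side by side (all values from Protocol 8.11)**

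| Measure | Action limit | Failure limit | Ratio |
|---|---|---|---|
| CFU/ml, dialysate | ≥50 | ≥100 | 50/100 = 0.5 |
| CFU/ml, water | ≥50 | ≥100 | 50/100 = 0.5 |
| EU/ml, dialysate | ≥0.50 | ≥0.50 | 0.50/0.50 = 1.0 |
| EU/ml, water | >0.25 | >0.25 | 0.25/0.25 = 1.0 |

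The inequality signs also match for endotoxin. Treatments between samples: 4 weeks × 4 per week = 16.

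The point rests on step 1 alone. The rest is illustration under my assumptions, because the documents give no drift rate, assay error or chance that a console reaches the limit.

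**2. Slow rise, no assay error**

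Let the level double every D weeks, with samples every 4 weeks and results acted on at once. The first sample after the level passes the limit falls on average 2 weeks later, so as written there are 2 × 4 = 8 treatments above the limit before any step. With a trigger at half the limit, the trigger level is passed D weeks sooner, and the mean is 4 × (4 − D)²/8 for D < 4, and 0 otherwise:

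- D = 1: 4 × 9/8 = 4.5
- D = 2: 4 × 4/8 = 2.0
- D ≥ 4: 0
- sudden rise (D = 0): 4 × 16/8 = 8, no gain

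These count treatments before any step. They equal exposure only if the triggered disinfection or log review ends the rise. If disinfection does not lower the level, a console that retests between trigger and limit stays in use and is caught at the same monthly sample as now. Simulation with 400,000 draws then gives 8.0 treatments to removal under either rule, for D from 1 to 8 weeks. The gain therefore lies anywhere from nothing to the full difference shown.

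**3. Assay error**

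Assume lognormal readings with CV 20% to 50%, s = √ln(1 + CV²), true level m as a fraction of the limit, two independent readings, and a level that disinfection leaves unchanged. Let a = 1 − Φ(ln(1/m)/s) be the chance of reading at or over the limit, and b = 1 − Φ(ln(0.5/m)/s) the chance of reading at or over half of it. Mandatory removal needs a² as written, and b × a with the lower trigger and removal kept at the existing limit.

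| True level | Removal as written | Removal with the change |
|---|---|---|
| 50% of limit | 0.0% to 0.5% | 0.0% to 3.6% |
| 75% | 0.5% to 7% | 7% to 22% |
| 90% | 9% to 17% | 30% to 37% |
| 120% | 42% to 67% | 63% to 82% |

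At 120% of the limit, one test prompts no step with probability 1 − a = 18% to 35% as written, against 1 − b = 0% to 3% with the change. Removal rises on both sides of the limit because one reading at the limit, after one at half of it, is now enough. The table leaves out removal at the sponsor's discretion after the first result.

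**4. Extra work**

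Assume 30 home consoles, two fluids, and 3 to 4 sampling times each (installation plus 2 to 3 monthly samples over 8 to 12 home weeks): 30 × 3 × 2 = 180 to 30 × 4 × 2 = 240 readings. The chance that a reading newly prompts action is b − a.

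- Consoles at 20% of the limit: 0 to 240 × (0.026 − 0.000) ≈ 6 extra triggers.
- Consoles at 30%: 180 × 0.005 ≈ 1 to 240 × (0.140 − 0.005) ≈ 32.

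In-center consoles would add to this.

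**The case against.** The strongest reply is that nothing in the documents requires a warning band for each measure, and that carrying the CFU ratio over to endotoxin is a choice. The response is also not absent: at the endotoxin limit the full sequence applies, failure status is discretionary, routine disinfection and filtration continue below the limit, and a CFU result of 50 or more prompts action by itself. All of that stands. It limits the weight of the point, but it does not supply an endotoxin-driven response below the failure limit.

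The second reply concerns benefit. The fall from 8 treatments to between 0 and 4.5 cannot be claimed together with disinfection that leaves the level unchanged, and the change would remove more compliant consoles. This also stands. Losing a home console matters, because 8.5 allows "no inter-dialytic (end of treatment period to start of next treatment period) period greater than 2 days" and the lost-to-follow-up rule in 7.6 begins "If the Subject fails to complete eight consecutive treatments". The point survives because 8.11 itself relies on chemical disinfection as its response, so prompting it sooner is consistent with the protocol's own logic.

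A reader might also infer that contaminated consoles go unaddressed, or that the equal limits are a drafting slip. The documents support neither: a response exists at the limit, and they do not say whether the equality is intended.

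**Conclusion.** The point holds as a minor patient-safety matter in device monitoring. That the endotoxin action tier has no margin is certain from the text. The size of any benefit is not: it depends on the triggered disinfection or log review being effective, and it is nil for a sudden rise or a level that does not fall. A reader might go further and infer bias in the primary safety result or a weakness in the sample size. The documents do not support that. The limits enter neither the adverse-event interval method, nor the Kt/V tests, nor the sample-size calculation.

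**What to change.** In 8.11, separate the endotoxin trigger from the removal limit.

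- **Trigger** for chemical disinfection, resampling and sponsor log review: ≥0.25 EU/ml dialysate and ≥0.125 EU/ml water, mirroring the CFU ratio. Confirm the assay's reportable range first. If the assay cannot report below 0.25 EU/ml, the water change is not available.
- **Mandatory removal after an endotoxin retest**: unchanged at ≥0.50 EU/ml dialysate and >0.25 EU/ml water. Lowering this as well would, in the model above, remove a console at half the limit in 0.5 × 0.5 = 25% of cases.
- **Retest between the two**: the console stays in use until the next monthly sample, unless the sponsor's log review decides otherwise.
- CFU limits and failure limits stay as they are.

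The cost is a protocol amendment with sponsor and IRB approval and training as appropriate (14.4), the extra cycles estimated in step 4 of the working, and somewhat more removals of consoles close to but under the limit. If the sponsor intended equal limits, a sentence in 8.11 giving the reason would at least settle the question.

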9 ADVERSE EVENT REPORTING

9.1 Adverse Event Definitions

9.1.1 Adverse Event (AE):

An adverse event (AE) is any undesirable medical occurrence in a clinical study Subject, whether it is considered to be related to the device or not, that includes a clinical sign, symptom or condition.

9.1.2 Serious Adverse Events (SAEs)

An AE is considered to be serious if it:

- results in death;
- is life-threatening;
- requires Subject hospitalization or prolongation of existing hospitalization;
- requires intervention to prevent permanent impairment or damage;
- results in persistent or significant disability/incapacity

9.1.3 Additional Treatment Observations (ATOs)

Additional Treatment Observations (ATOs) are observations of interest that are not considered adverse events. These observations will be recorded as measured. These include, but are not limited to:

- Blood pressure measurements
- Phosphorous and potassium levels
- Alarms that end treatment
- Subjects feeling cold during treatment
- Study Subject drop out
- clinically significant alarms during treatment as reported by the Tablo Console
 - air in venous bloodline,
 - low systolic blood pressure,
 - high/low venous pressure, and
 - o blood leak in dialyzer

9.1.4 Unanticipated Adverse Device Effects (UADEs)

An unanticipated Adverse Device Effect means any serious adverse effect on health or safety or any lifethreatening problem or death caused by, or associated with, a device, if that effect, problem, or death was not previously identified in nature, severity, or degree of incidence in the investigational plan or application (including a supplementary plan or application), or any other unanticipated serious problem associated with a device that relates to the rights, safety, or welfare of Subjects.

